2. STUDY OBJECTIVES

2.1 **Primary objective**

The primary objective of this study is to assess the efficacy of D20 once daily (q.d.) versus placebo in continuous treatment involving patients with a history of gastric and/or duodenal ulcers receiving daily LDA therapy by evaluating time from randomisation to occurrence of gastric and/or duodenal ulcers.

2.2 Secondary objectives

The secondary objectives of this study are to assess the efficacy of D20 versus placebo in patients with a history of gastric and/or duodenal ulcer receiving daily LDA therapy by evaluating the following:

- Presence/absence of gastric and/or duodenal ulcers up to 12, 24, 36, 48, 60 and 72 weeks after randomisation
- Degree of gastric mucosal lesion evaluated by modified LANZA score (Lanza FL et al 1988) at Weeks 12, 24, 36, 48, 60 and 72 after randomisation
- Presence/absence and severity of reflux esophagitis (RE) evaluated by the Los Angeles (LA) classification (Lundell LR et al 1999) at Weeks 12, 24, 36, 48, 60 and 72 after randomisation
- Presence /absence and severity of gastrointestinal symptoms assessed by investigator(s) at each visit

2.3 Exploratory objective

The exploratory objective of this study is to investigate the effect of CYP2C19 polymorphism on the efficacy of D20 in patients with a history of gastric and/or duodenal ulcer receiving daily LDA therapy by evaluating the primary and secondary efficacy outcome variables separately for CYP2C19 genotypes.

2.4 Safety objective

- Safety
 - To assess safety and tolerability of D20 versus placebo in patients with a history of gastric and/or duodenal ulcers on continuous LDA therapy by evaluating adverse events, clinical laboratory data, and vital signs (blood pressure and pulse rate).
- Long term safety
 - To assess long-term safety and tolerability of D20 during long-term treatment (52 weeks or longer) in patients (100 or more) with a history of gastric and/or duodenal ulcers on continuous LDA therapy by evaluating adverse events, clinical laboratory data, and vital signs (blood pressure and pulse rate).

3. STUDY PLAN AND PROCEDURES

This Clinical Study Protocol has been subject to a peer review according to AstraZeneca standard procedures.

3.1 Overall study design and flow chart

This study is designed as a multinational, multicenter, randomized, double-blind, parallelgroup (2 groups), placebo controlled, Phase III study involving patients with a history of gastric and/or duodenal ulcers receiving daily LDA therapy. A total of 426 patients with a history of gastric and/or duodenal ulcers with ulcer scar confirmed by the esophagogastroduodenoscopy (EGD) performed at screening will be randomized 1:1 to either D20 group or placebo group. The efficacy and safety of D20 or placebo will be assessed after up to 72-week oral administration based on the results of the EGD performed at Weeks 12, 24, 36, 48, 60 and 72 after randomisation to verify presence or absence of gastric and/or duodenal ulcers, modified LANZA score to evaluate the degree of gastric and/or duodenal mucosal lesion and presence/absence and severity of RE evaluated by LA classification, and investigator's assessment for presence/absence and severity of gastrointestinal symptoms performed every 4 weeks. In addition, the safety of the concomitant use of D961H and LDA for a long-term period will be confirmed. If development of gastric and/or duodenal ulcer was observed in 36 patients, data will be cut off and analysed. Therefore, it is speculated to administer the test product for up to 72 weeks, but the period of administration of test product may not reach 72 weeks. (See Figure 1)

When development of gastric and/or duodenal ulcer was observed in at least 18 patients and at least 250 patients were randomized, the interim analysis will be performed by an independent data monitoring committee (IDMC) following the data cut-off, data cleaning and data base lock for the analysis. IDMC will decide on a recommendation on continuing or discontinuing the comparative analysis based on the results of the interim analysis (See Section 12.2.3). If IDMC recommend to continue the study, a final comparative analysis will be performed when development of gastric and/or duodenal ulcer is observed in at least 36 patients following the data cut-off, data cleaning and the database lock.

The sponsor will count the number of subjects in the D20 groups who have completed the tests at Visit 15 (Week 52) quickly after the completion of the comparative analysis (including the completion by the interim analysis).

If the number is 100 or more, the sponsor will report the termination of the study to the investigator(s). The investigator(s) will perform the tests required for Visit 20 to all subjects at the next visit after receiving the report and will make the subjects complete the study.

If the number is less than 100, the sponsor will report the continuation of the study and the key information of each subject at the site to the investigator(s). The investigator(s) will perform the tests required at Visit 20 to subjects who are randomised to placebo at the next visit after receiving the report and will make the subjects complete the study. For subjects who are randomised to D20, if the next visit after receiving the report is Visit 15 (Week 52) or later, the investigator(s) will perform the tests required for Visit 20 to the corresponding subjects at the visit and will make the subjects complete the study. If the next visit after receiving the report is before Visit 15 (Week 52), the investigator(s) will perform the tests required at the visit and make the subjects continue the study until Visit 15 (Week 52) after confirming that the subjects want to continue the investigational treatment. If subjects do not want to continue

the investigational treatment, then the investigator(s) will perform the tests required for Visit 20 and will make the subjects complete the study at the visit. The sponsor will report the termination of the study to the investigator(s) as soon as the number of subjects in the D20 group who have completed Visit 15 is reached 100 or more. The investigator(s) will perform the tests required for Visit 20 to all subjects at the next visit after receiving the report and will make the subjects complete the study.

EGD findings judged as an evidence of an ulcer scar at screening, those previously confirmed as ulcers and those judged as gastric and/or duodenal ulcers by the investigator(s) after randomisation as gastric and/or duodenal ulcers will be reviewed by the central evaluation committee (see Section 12.4) established by the sponsor under the blinded conditions any time.

Figure 2 shows the study design and Table 2 shows the study plan including frequency and time of visits.

*1 Investigators notice the study completion to the subjects, if applicable, at the next visit after the key broken. (See Section 5.8.2)

Table 2Study plan

Period	Screenin	aing Study treatment																		
		Rand omiz ation																		
Visit	1	2	3	4	5	6	7	8	9	10	11	12	13	14	15	16	17	18	19	20 (Compl etion/ Withdr awal) l
No. of weeks from Visit 2	- 2 W to 0 W	0 W	4 W	8 W	12 W	16 W	20 W	24 W	28 W	32 W	36 W	40 W	44 W	48 W	52 W	56 W	60 W	64 W	68 W	72 W
Visit window (day)	-	-	± 4	± 4	± 7	±7														
Informed consent ^a	Х																			
Inclusion/exclusion criteria	Х	Х																		
Demographic data ^b	Х																			
Medical/surgical history ^b	Х																			
Concomitant disease	Х	Х																		
Height, Weight	Х																			
Physical examination	Х	Х	Х	Х	Х	Х	Х	Х	Х	Х	Х	Х	Х	Х	Х	Х	Х	Х	Х	Х
Vital signs (blood pressure and pulse rate)	Х		Х	Х	Х	Х	Х	Х	Х	Х	Х	Х	Х	Х	Х	Х	Х	Х	Х	Х
Clinical laboratory tests ^c																				
- Haematology tests ^d	Х		Х	Х	Х	Х	Х	Х	Х	Х	Х	Х	Х	Х	Х	Х	Х	Х	Х	Х
- Biochemistry tests	Х				Х			Х			Х			Х			Х			Х
- Urine tests	Х				Х			Х			Х			Х			Х			Х
Pregnancy test (urine) ^e	Х																			

Table 2Study plan

Period	Screenir	Study treatment																		
		Rand omiz ation																		
Visit	1	2	3	4	5	6	7	8	9	10	11	12	13	14	15	16	17	18	19	20 (Compl etion/ Withdr awal) l
No. of weeks from Visit 2	- 2 W to 0 W	0 W	4 W	8 W	12 W	16 W	20 W	24 W	28 W	32 W	36 W	40 W	44 W	48 W	52 W	56 W	60 W	64 W	68 W	72 W
Visit window (day)	-	-	± 4	± 4	± 7	± 7														
H. Pylo ri test (IgG antibody)		X ^m																		
Genetic test for CYP2C19		X^m																		
EGD ^{d,f}																				
- Confirmation of presence/absence of gastric and/or duodenal ulcer	X ⁿ				Х			Х			Х			Х			Х			X°
- Assessment of degree of gastric mucosal lesions ^g	X^n				Х			Х			Х			Х			Х			X°
- Confirmation of presence/absence and severity of RE ^h	X^n				Х			Х			Х			Х			Х			X°
- Assessment of gastric mucosa	X^n																			

Table 2Study plan

Period	Screenin	Stu	dy tre	atmei	nt															
		Rand omiz ation																		
Visit	1	2	3	4	5	6	7	8	9	10	11	12	13	14	15	16	17	18	19	20 (Compl etion/ Withdr awal) l
No. of weeks from Visit 2	- 2 W to 0 W	0 W	4 W	8 W	12 W	16 W	20 W	24 W	28 W	32 W	36 W	40 W	44 W	48 W	52 W	56 W	60 W	64 W	68 W	72 W
Visit window (day)	-	-	± 4	± 4	± 7	± 7														
Evaluation of LDA- associated gastrointestinal symptoms by the investigator ⁱ		Х	Х	Х	Х	Х	Х	Х	Х	Х	Х	Х	Х	Х	Х	Х	Х	Х	Х	Х
Randomization		Х																		
Dispense the investigational products and mucosal protectant		Х	Х	Х	Х	Х	Х	Х	Х	Х	Х	Х	Х	Х	Х	Х	Х	Х	Х	
Confirm/collect the remaining investigational products and mucosal protectant			Х	Х	Х	Х	Х	Х	Х	Х	Х	Х	Х	Х	Х	Х	Х	Х	Х	Х
Compliance status of D961H, mucosal protectant and LDA ^j			Х	Х	Х	Х	Х	Х	Х	Х	Х	Х	Х	Х	Х	Х	Х	Х	Х	Х
AE confirmation ^k	Х	Х	Х	Х	Х	Х	Х	Х	Х	Х	Х	Х	Х	Х	Х	Х	Х	Х	Х	Х
Concomitant therapy/drug	Х	Х	Х	Х	Х	Х	Х	Х	Х	Х	Х	Х	Х	Х	Х	Х	Х	Х	Х	Х

- a. Should be obtained within 4 weeks prior to Visit 2 (randomization). Regarding EGD result for screening, see footnote m.
- b. For the variables for demographic and disease history data, see Section 6.2.1.
- c. Clinical laboratory tests will be conducted at the local laboratory.
- d. The subject must be fasting.
- e. Pregnancy test will be conducted for premenopausal women of childbearing potential.
- f. Visit allowance for EGD is ± 14 days.
- g. According to the modified LANZA score.
- h. According to the LA classification.
- i. The subject will complete the medical interview form (see Appendix E) at each visit and the investigator(s) will confirm the contents of the form to assess severity of each symptom based on the severity classification.
- j. The investigators will confirm the compliance of D961H, mucosal protectant and LDA. Regarding LDA, the subjects will be instructed to record compliance of taking LDA in the compliance record (see Appendix F) and bring it at each visit for confirmation of the compliance.
- k. From obtained informed consent until randomisation, only SAEs will be collected and recorded in the eCRF. For AEs other than SAEs only those occurring from the randomization date (Visit 2) to the last scheduled visit or withdrawal will be recorded in the eCRF.
- 1. If the subject discontinues the study before completing the treatment period (72 weeks), the subject should undergo the tests planned for Visit 20 (Week 72) as much as possible.
- m. The samples will be measured at the central laboratory. As a general rule, these tests were done at visit 2. However, if these tests were missed at visit 2, though they can be done at any visit until discontinuation/completion of the study, *H. pylori* test (IgG antibody) and CYP2C19 should be done at same visit as a general rule.
- n. EGD obtained before informed consent date can be used with the consent of the subjects, if the EGD was conducted within 2 weeks prior to the randomization.
- o. EGD for placebo arm study completion after the key broken is voluntary.

3.2 Rationale for study design, doses and control groups

Rationale for target subject population

In the Guidelines for Diagnosis and Treatment of Gastric Ulcer Based on the EBM (Guidelines for Diagnosis and Treatment of Gastric Ulcer Based on the EBM 2007), a history of gastric and/or duodenal ulcers is considered one of the certain risk factors in peptic ulcer induced with NSAIDs including LDA and taken similarly as a risk factor in various academic societies in U.S.A. (Bhatt DL et al 2008) and research groups in Asia Pacific area (Sung J et al 2000). Based on these, "patients with a history of gastric and/or duodenal ulcers" was established as a target population.

Rationale for D961H dose setting

In overseas, the clinical study of once daily administration of D20, D40 and placebo to investigate this indication has been completed and submitted for NDA in the U.S.. The planned doses for prevention of peptic ulcer in patients on LDA treatment are 20 and 40 mg once daily in the U.S.. In the Japanese Phase I study, acid inhibitory effect was evaluated by CYP2C19 genotype, using percentage of time with intragastric pH4>during the 24-hour intragastric pH monitoring in healthy male subjects who received orally the study medication once daily for 5 days. The doses studied were 10 mg, 20 mg and 40 mg. As a result, percentage of time with intragastric pH4> was lower in homo Extensive Metabolizer (EM) patients as compared with hetero EM and Poor Metabolizer (PM) patients at 10 mg. This suggests that 10 mg dose provides weak acid inhibitory effect to homo EM patients thereby provides only insufficient clinical efficacy in these patients. It is reported that the risk factors for LDA-induced peptic ulcer include history of peptic ulcer, concomitant use of anticoagulant, concomitant use of anti-platelets, elderly patients, concomitant use of steroids, concomitant use of other NSAIDs (Bhatt DL et al 2008). Treatment with LDA needs to be continued for long (life-long) and over time, new risk factors for peptic ulcer will be added. Some patients receiving LDA treatment may abruptly present hematemesis or tarry stool without gastrointestinal symptoms such as abdominal pain and diagnosis peptic ulcer and/or gastrointestinal bleeding followed by serious conditions. Careful monitoring of the patients is, therefore, necessary. In addition to D961H acid inhibitory effect at different doses, characteristics of LDA-induced peptic ulcer and its prognosis need to be considered for D961H dose setting for combination use with LDA. This study, therefore, will not include 10 mg. Since the clinical dose of D961H for peptic ulcer treatment is planned to be 20 mg. doses above 20 mg was not considered necessary to investigate the possible clinical doses for prevention of peptic ulcer.

Rationale for setting the control group

The target indication of D961H is "Prevention of gastric or duodenal ulcer associated with low dose aspirin," since there is no drug approved for this indication in Japan, Korea and Taiwan, placebo was selected as the control to D961H.

Rationale for setting mucosal protectants

The patient population in this study is including elderly patients and those with high risk of peptic ulcer due to continuous use of LDA. The majority of these patients receive treatment with mucosal protectants in General Practice. Therefore, it was decided to treat all patients in the study with the mucosal protectant. And the most mucosal protectants are taken three times daily, but Gefarnate 50 mg is taken twice daily. So it was decided to take mucosal protectant, Gefarnate 50 mg, twice daily continuously in all the patients as considering drug compliance.

Rationale for length of study

LDA treatment is expected to be continuous to prevent thrombosis/embolism. It is considered that no fixed treatment length needs to be defined for each patient, to investigate LDA-induced peptic ulcer prevention, and thus, it was defined as a maximum of 72 weeks, since it seems possible to evaluate presence/absence of peptic ulcer development during this period.

Furthermore, at least 100 patients randomized to D20 group will continue the treatment for 52 weeks, because ICH E1 guideline requires safety data of 100 patients for 1 year is required.

Rationale for endpoint setting

The target population of this study is a set of subjects who have a history of gastric and/or duodenal ulcers. These subjects have high risk of recurrence of gastric and/or duodenal ulcers due to continuous use of LDA. In order to verify the efficacy of D20 for the prevention of the occurrence, it is important to show that D20 prolongs time to occurrence so that D20 decreases the number of subjects who have a occurrence of gastric and/or duodenal ulcer. Therefore, time from randomisation to a occurrence of gastric and/or duodenal ulcer confirmed by EGD was adopted as a primary outcome variable.

Rationale for a genetic test

D961H is mainly metabolized by CYP2C19 known as being polymorphic genotype, therefore, it is assumed that the clinical effect of D961H may be influenced by polymorphism of CYP2C19 gene. In this study the influence of genotype in the patients receiving long-term concomitant treatment with D961H and LDA will be examined and thus a genetic test of CYP2C19 gene is included.

Rationale for an H. pylori test setting

As concerns LDA-induced peptic ulcer, prevention of occurrence by removal of *H. pylori* was shown in the randomised controlled trial (Chan FK et al 2001). However, it is reported that the incidence of subsequent recurrence of gastric ulcer was high as 46.7% with removal of *H. Pylori* + placebo but significantly inhibited as 5.6% with removal of *H. Pylori* + PPI (Lai KC et al 2002). Moreover, the results of the investigation showed that recurrence rates of gastric ulcers in the three treatment groups of patients with history of *H. Pylori* negative gastric ulcer, *H. Pylori* positive gastric ulcer, and *H. Pylori* eradicated gastric ulcer showed no significant difference between the three groups (Bianchi Porro G et al 1996). Accordingly, since prevention of occurrence by the treatment by removal of *H. pylori* alone is controversial, it is considered necessary to conduct a versatile study to investigate the relationship between *H*.

pylori infection and peptic ulcers induced with NSAID including LDA. Based on the above, information on presence or absence of history of *H. pylori* infection will be collected in this study as a part of demographic data.

4. SUBJECT SELECTION CRITERIA

Investigator(s) should keep a record, the subject screening log, of subjects who entered prestudy screening after getting informed consent.

Each subject should meet all of the inclusion criteria and none of the exclusion criteria for this study.

4.1 Inclusion criteria

For inclusion in the study subjects should fulfil the following criteria:

- 1. Provision of written informed consent before starting the study-related procedures and examinations (including written informed consent to a genetic test)
- 2. Medical history of gastric and/or duodenal ulcer. This is defined as the presence of a gastric or duodenal ulcer scar confirmed by EGD findings obtained within two weeks prior to the randomization. The test data obtained before informed consent can be used with the consent of the subjects, if the test was conducted within two weeks prior to the randomization. In the case that the results of the test did not demonstrate the scar clearly but the subject had an evidence of ulcer confirmed by EGD performed in the past he/she will be eligible. If the finding shown below was obtained by EGD, it should be considered the ulcer scar to be present. "The condition in which ulcer-induced tissue defect is restored by exuberant granulation of regenerating epithelium, and the scar of healed ulcer and deformation. Including both red scar (redness is observed in the mucosa of scar) and white scar (the mucosa of scar showing the same color tone as the surrounding mucosa)."
- 3. A diagnosis of a chronic condition (angina pectoris, myocardial infarction and ischemic cerebrovascular disorder, etc., requiring prevention of thrombosis or embolism) that is taking the prescribed LDA of at least 5 out of 7 days each week during the study treatment period.
 - Dose of LDA is 81 mg to 324 mg per day.

4.2 Exclusion criteria

Subjects should not enter the study if any of the following exclusion criteria are fulfilled:

- 1. Less than 20 years of age at the time of informed consent.
- 2. Having gastric or duodenal ulcer (except for ulcer scar).
- 3. History of esophageal, gastric or duodenal surgery, except for simple closure of perforation.

- 4. Having severe liver disease or liver enzyme (AST [GOT], ALT [GPT], or ALP) or the total bilirubin level three times the upper limit of reference values at laboratory tests conducted within 2 weeks prior to randomization.
- 5. Having a chronic renal disease or impaired renal function or serum creatinine level two times the upper limit of reference values at laboratory test conducted within 2 weeks prior to randomization
- 6. Current or historical evidence of the following diseases/conditions:
 - (i) Zollinger-Ellison syndrome
 - (ii) Inflammatory bowel disease (IBD)
 - (iii) EGD evidence or suspicion (not LDA-induced) of pathological or infiltrative process in gastric and/or duodenum (e.g., Crohn's disease, malignancy, sarcoidosis, amyloidosis, ischemic disease)
 - (iv) Serious cardiac failure: New York Heart Association Functional Classification III – IV (NYHA III – IV), or left ventricular Ejection Fraction (EF) <40%
- 7. Any condition that requires surgery during the study period (from the day of informed consent to the day of the last scheduled visit or discontinuation)
- 8. History of malignant disease within 5 years before randomization. Mild superficial cutaneous disease is allowed.
- 9. Current or historical evidence (within 12 weeks prior to randomization) of the following disease/conditions:
 - (i) Malabsorption syndrome
 - (ii) Esophageal stricture
 - (iii) RE (LA classification grade A to D)
 - (iv) Dysplastic changes (based on the documented findings) of any grade in the gastrointestinal tract
 - (v) Signs and symptoms of gastric outlet obstruction (e.g., abdominal distension or multiple episodes of vomiting)
 - (vi) Pancreatitis
 - (vii) Severe pulmonary disease
 - (viii) Diabetes mellitus uncontrolled on dietary management, exercise therapy or medication
 - (ix) Unstable hypertension

- (x) Acute coronary syndrome
- (xi) Cerebrovascular accident (if occur)
- (xii) Pregnancy or lactation. Women of childbearing potential must have a positive urine pregnancy test at screening.
- 10. Use of any other investigational compounds or participation in another clinical study within 4 weeks prior to randomization
- 11. Prior randomized in the study. However, subjects who fulfil the followings and agree to provide informed consent for the second time can be re-enrolled:
 - Subjects who are confirmed having gastric or duodenal ulcer by EGD at screening can be enrolled if the subjects are confirmed healing.
 - Subjects who have not been confirmed having gastric or duodenal ulcer scar by EGD at screening can be enrolled if the subjects are confirmed having ulcer scar and provide informed consent again. The previous EGD must be performed equal to or more than 12 weeks before.
- 12. Need for continuous concomitant therapy with:
 - (i) PPI (except for the investigational product)
 - (ii) H2-receptor antagonists
 - (iii) M1-receptor antagonists
 - (iv) *H. pylori* eradication therapy
 - (v) Antacids
 - (vi) Prostaglandin analogue indicated for peptic ulcers e.g. Misoprostol)
 - (vii) Drugs with systemic anticholinergic effects
 - (viii) Gastrointestinal promotility drugs
 - (ix) Any drug known to have drug-drug interactions with D961H and/or OPZ,
 (e.g. atasanavir sulphate, diazepam, phenytoin, warfarin, tacrolimus hydrate, digoxin, methyldigoxin, itraconazole, gefitinib, voriconazole)
 - (x) Anticancer drugs
 - (xi) Continuous NSAID therapy (oral, intravenous, intramuscular or suppository)
 Use of NSAIDs within 7 consecutive days will be allowed.

- (xii) Anticoagulants (warfarin, vitamin K antagonists, heparin, lowmolecular weight heparin, anti-thrombin drug or anti Xa drug)
- 13. Any significant "alarm symptoms" within the past 24 weeks before randomization, such as, unintentional weight loss, gastrointestinal bleeding, jaundice, or any other sign indicating serious or malignant disease.
- 14. Subjects with disease/symptom allowing no administration of study drugs, such as known or suspected allergy or sensitivity to proton pump inhibitor.
- 15. Any history of a generalized bleeding disorder resulting from hemorrhagic diathesis (e.g., abnormalities in clotting factors or platelets)
- 16. History of drug addiction or alcoholism within the past 12 months prior to randomization.
- 17. Inability to understand or provide informed consent.
- 18. Inability or unwillingness to take study medication according to dosing instructions.
- 19. Inability to undergo EGD, or unwillingness to undergo multiple endoscopies.
- 20. Involvement in the planning and conduct of the study (applies to both sponsor staff or staff at the study site).
- 21. Subjects who, for whatever reason are unlikely to comply with study requirements as judged by the investigators.

Procedures for withdrawal of incorrectly enrolled subjects see Section 5.3.

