5. STUDY CONDUCT

5.1 **Restrictions during the study**

The patients should observe the following items during the study.

- 1. The subject must fast before blood sampling for biochemistry test and undergoing EGD according to the procedures specified by the study centre.
- 2. 50 mg of gefarnate should be taken orally twice a day from randomized day to the last day of scheduled visit or day of discontinuation.
- 3. The subject must not stop the dosing temporarily and change the dose of LDA from informed consent day to the last day of scheduled visit or study discontinuation. As an exception, if the investigators judge that the temporarily stop dosing is necessary for treatments, e.g. biopsy, the subject can stop the LDA dosing temporality within consecutive 7 days.
- 4. The subject must maintain effective contraception from informed consent day to the last day of scheduled visit or day of discontinuation as judged by the investigator(s) during the study period.
- 5. The subject must not donate blood from informed consent day to the last day of scheduled visit or day of discontinuation.

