5.2 Subject enrolment and randomisation method

The Principal Investigator will:

- 1. Obtain signed informed consent from the potential subject before any study specific procedures are performed.
- 2. Assign potential subject a unique enrolment number, beginning with 'E'. The Enrolment code (EXXXXYYY) is composed of 4 digits (XXXX) of centre number and 3 digits (YYY) of consecutive number in order of registration to screening at each study site. For the subjects who are confirmed having gastric and/or duodenal ulcer by EGD at screening and re-enrolled after the subjects are confirmed healing and provide informed consent for the second time, the number added 500 to the previous consecutive number (YYY) will be allocated. The number added 600, 700, 800 and 900 will be allocated at the third, the fourth, the fifth and sixth time correspondingly. For centre number(s), see Appendix A "Investigators and Study Administrative Structure".
- 3. Determine subject eligibility. See Sections 4.1 and 4.2
- 4. If the subject is eligible, the investigator(s) will enter the necessary information in the subject registration form via the subject registration Web system.
- 5. The subject registration will be completed after the eligibility checks by the subject registration Web system. A randomization code (Subject number) will be allocated automatically and will be shown on the screen in the Web system.
- 6. After obtaining the randomisation code (Subject number), the investigator(s) will start administration of the investigational product to the registered subject. The investigator(s) will print out the registration confirmation form and keep in the investigator's study file (See Section 9.4.1)

If a subject withdraws from participation in the study, then his/her enrolment/randomisation code cannot be reused.

The flowchart for subject registration, randomisation and prescription of the investigational product is shown in Figure 3.

Figure 3 Flow chart for subject registration and prescription of the investigational product

Procedure conducted at the study site

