5.8 Discontinuation of investigational product

The study treatment and assessments can be discontinued at any time.

Specific reasons for discontinuing a subject from this study are:

- Voluntary discontinuation by the subject who is at any time free to discontinue his/her participation in the study, without prejudice to further treatment
- Safety reasons as judged by the investigator(s) and/or AstraZeneca
- Severe non-compliance to protocol as judged by the investigator(s) and/or AstraZeneca
- Incorrect enrolment i.e., the subject does not meet the required inclusion/exclusion criteria for the study except for the cases that the AstraZeneca Study Delivery Team Physician and the Investigator reach an agreement to continue the study as the result of the discussion. (See also Section 5.3)
- Subject lost to follow-up
- Occurrence of an event in conflict of exclusion criteria (e.g., pregnancy)
- Development of gastric and/or duodenal ulcer
- Difficulty to conduct the study as judged by the investigator(s) due to the presence of gastric and/or duodenal mucosal lesion such as bleeding.
- Stopping treatment with daily LDA
- Others as judged appropriate by the investigator(s) (reasons for discontinuation must be documented in the eCRF appropriately)

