6.2 Data collection and enrolment

6.2.1 Recording of demographic characteristics and screening test

The data on the following demographic characteristics and the screening test are collected, and recorded in eCRF.

Visit 1 (within 2 weeks of randomization)

- Patient background (sex, date of birth, race, smoking habit or not, drinking habit or not, height, body weight)
- Primary disease (disease that requires continued LDA administration), history of ulcer (presence or absence of definite diagnosis in the past), history of *H. pylori* eradication, history of disease (critical symptom & finding in the past, though currently cured), incidental disease (disease currently under treatment [including the disease that is controlled by treatment]), history of operation, concomitant therapy & concomitant drug
- Physical findings, vital signs (blood pressure and pulse rate)

- EGD (see Section 6.2.2. The test results obtained by 2 weeks before randomization but before acquisition of informed consent may be used if the consent in this regard is obtained.)
- Blood test, blood biochemical test
- Urine tests
- Pregnancy test by urinalysis (hCG) (only the fertile females before menopause)

Visit 2 (randomization day)

- Physical findings
- Assessment of gastrointestinal symptoms attributable to LDA in the past 7 days (Section 6.3.4)
- *H. pylori* test (see Section 6.2.3)
- CYP2C19 gene test (see Section 6.8)
- Adverse events, incidental disease
- Concomitant therapy & concomitant drugs

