13.3.1 Maternal exposure

If a subject becomes pregnant during the course of the study investigational product should be discontinued immediately.

Pregnancy itself is not regarded as an adverse event unless there is a suspicion that the investigational product under study may have interfered with the effectiveness of a contraceptive medication. Congenital abnormalities/birth defects and spontaneous miscarriages should be reported and handled as SAEs. Elective abortions without complications should not be handled as AEs. The outcome of all pregnancies (spontaneous miscarriage, elective termination, ectopic pregnancy, normal birth or congenital abnormality) should be followed up and documented even if the subject was discontinued from the study. The PREGREP module in the eCRF is used to report the pregnancy and the PREGOUT is used to report the outcome of the pregnancy.

If any pregnancy occurs in the course of the study, then investigators or other site personnel inform appropriate AstraZeneca representatives **within one day** ie, immediately but no later than the **end of the next business day** of when he or she becomes aware of it.

The designated AstraZeneca representative works with the investigator to ensure that all relevant information is provided to the AstraZeneca Patient Safety data entry site within 1 or 5 days for SAEs, see Section 6.4.4 and within 30 days for all other pregnancies.

The same timelines apply when outcome information is available.

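### Exclusion criterion 9 (xii) bars pregnancy and then requires a positive urine pregnancy test; no other part of the protocol states the qualifying result.

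*Protocol*

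**What the plan says.** Section 4 requires each subject to meet every inclusion criterion and no exclusion criterion. Exclusion 9 (xii) in Section 4.2 has two sentences. The first names the excluded condition: "Pregnancy or lactation". The second sets a test requirement: "Women of childbearing potential must have a positive urine pregnancy test at screening".

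The urine test is mentioned in three other places:

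- The Table 2 row in Section 3.1 marks it at Visit 1 only.
- Footnote e to that table says: "Pregnancy test will be conducted for premenopausal women of childbearing potential".
- The Visit 1 list in Section 6.2.1 names the urine hCG test and limits it to premenopausal women who are fertile.

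Three further sections deal with pregnancy or its prevention. Section 5.1 sets a restriction for the study period: "The subject must maintain effective contraception from informed consent day". Section 5.8 lists pregnancy among the reasons for discontinuation, as an event that conflicts with the exclusion criteria. Section 13.3.1 says: "If a subject becomes pregnant during the course of the study investigational product should be discontinued immediately".

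**The concern.** The second sentence of 9 (xii) requires the result that indicates the condition excluded by the first. It is also the only sentence in the protocol that states a required test result, so a reader cannot look elsewhere for the correct one.

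This is a working eligibility and subject-protection rule. Section 5.3 says that subjects who fail the criteria must never be enrolled or randomised and allows no exceptions. Section 9.4.2 requires investigators in Japan to document every protocol deviation. A site that sensibly enrols a woman with a negative test therefore acts against the literal text. A site that applies the sentence strictly turns away every non-pregnant woman of childbearing potential.

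Registration also runs through an automated step: "The subject registration will be completed after the eligibility checks by the subject registration Web system". The rule in that system should derive from unambiguous text. The protocol does not show whether the error was carried into it.

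**Working it through.** No arithmetic applies. The check has three parts.

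**1. Apply both sentences of 9 (xii) to each possible result for a woman of childbearing potential.**

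| Urine test at screening | First sentence (pregnancy excludes) | Second sentence (must be positive) | Eligible as written? |
|---|---|---|---|
| Positive | Excluded, as the test indicates pregnancy | Met | No |
| Negative | Not excluded | Not met | No |

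Neither of the two results leads to eligibility. The only literal escape would be a false positive in a woman who is not pregnant, which cannot have been intended.

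With *negative* in place of *positive*, the second row meets both sentences and the first row fails both. The contradiction is gone.

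**2. Look for the qualifying result elsewhere.**

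| Place | Who is tested | When | Result required |
|---|---|---|---|
| Table 2 row, Section 3.1 | via footnote e | Visit 1 | not stated |
| Table 2 footnote e | premenopausal women of childbearing potential | not stated | not stated |
| Section 6.2.1 | fertile premenopausal women | Visit 1 | not stated |

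None of the three gives the result, so Section 4.2 is the sole statement of it. The test is scheduled at 1 of 20 visits, so this is the only scheduled test for pregnancy before or during treatment of up to 72 weeks.

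**3. Establish the intent.** Section 5.1 (contraception), Section 5.8 (pregnancy as a conflict with the exclusion criteria) and Section 13.3.1 (product stopped at once on pregnancy) all point the same way: pregnant women are not to receive study drug. None of them says that the screening test must be negative, but that is the only result consistent with all three.

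**The case against.** The strongest reply accepts that the word is wrong and disputes its weight.

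- **No pregnant woman is admitted.** The first words of 9 (xii) stop anyone who is pregnant, whatever the second sentence says. Applied literally and in full, the item can only keep out women who should be eligible. This stands. The realistic risk is confusion or over-exclusion at a site, and fetal exposure is not shown.
- **The intent is obvious.** A urine hCG test placed beside a pregnancy exclusion is there to detect pregnancy, and the other sections confirm it. This also stands, and it makes a drafting slip the likely explanation. It does not make the sentence correct, because Section 5.3 leaves sites no discretion to read a criterion against its wording.
- **Under an exclusion heading the sentence may mean that a positive test excludes.** This does not stand. The verb phrase expresses a requirement on the woman, not a condition that bars her.
- **The web-system point is speculative.** It stands as far as evidence goes, since the system's rules are not in the protocol. It supports a precautionary check and no more.
- **Nothing statistical depends on it.** This stands. Removal from the per-protocol set is not shown either, because Section 12.1.1 ties it to serious deviations or violations.

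**Conclusion.** The concern holds. Exclusion 9 (xii) contradicts itself, and the wrong word sits in the only sentence that states which test result qualifies. It should be corrected because it is an operative eligibility rule at about 60 centres in three countries, not because it threatens the trial's conclusions.

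Its size is one word in one criterion. The planned 426 subjects, the 36 events, the 2.94% significance level, the power and the primary analysis on the full analysis set are unaffected.

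The protocol does not say how many women of childbearing potential are expected. That the number is small is an assumption, consistent with a population on long-term aspirin for thrombosis prevention that includes elderly patients. It cannot be taken as zero, since entry is open from age 20 and the protocol schedules the test for such women. The conclusion rests on the wording alone and does not depend on that number.

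**What to change.** In Section 4.2, exclusion 9 (xii), replace *positive* with *negative* in the second sentence and leave the rest of the item as it is. Make the change through the Section 8.5 amendment route and notify the sites. Confirm once that the eligibility check in the registration web system treats a negative result as qualifying.

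The cost is a one-word amendment with the approvals that Section 8.5 requires, a notice to about 60 centres, and one system check. There is no statistical cost.
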